**Table 1: Schedule of Infusion Sessions**

Study Phase	Session Number	Study Day	Infusions (2 mL over 1 minute)
Screening	1	-2	20 mg cocaine, followed by a saline infusion, followed by 40 mg cocaine*
Baseline	2	1	Saline or 20 mg cocaine followed by either 20 mg cocaine or saline*
Baseline	3	2	Saline or 40 mg cocaine followed by either 40 mg cocaine or saline*
Treatment	4	8	Saline or 20 mg cocaine followed by either 20 mg cocaine or saline* †
Treatment	5	9	Saline or 40 mg cocaine followed by either 40 mg cocaine or saline* ‡

* Infusions will be administered 60 minutes apart.  † The order of cocaine or saline will match the order established during Infusion Session 2 (Day 1).  ‡ The order of cocaine or saline will match the order established during Infusion Session 3 (Day 2).
			

**Figure 1: Study Schema**

Study Day	Study Procedures
Days -28 to -4	Screening
Day -3	Clinic intake
Day -2	Screening Infusion Session #1 : 20 mg cocaine → Saline → 40 mg cocaine
Day -1	Randomization
Day 1	Baseline Infusion Session #2 : Session #2: Saline & 20 mg cocaine
Day 2	Baseline Infusion Session #3 : Saline & 40 mg cocaine
Days 3 to 9	SXC-2023 or placebo administration QD
Day 8	Infusion Session #4 : Saline & 20 mg cocaine
Day 9	Infusion Session #5 : Saline & 40 mg cocaine
Day 11	Clinic Discharge
Days 18 to 21	Final Follow-up

## 7 PARTICIPANT SELECTION

### 7.1 Inclusion Criteria

In order to participate in the study, participants must:

1. Be participants who are cocaine-experienced and not seeking treatment for cocaine use disorder.
2. Males and females between 18 and 59 years of age, inclusive.
  - The masculine / feminine gender is used without any discrimination and with the aim to lighten the text.
3. Have a body mass index (BMI) within a range of 17.0 to 36.0 kg/m^2 and a minimum weight of at least 50.0 kg at screening.
4. Have experience using cocaine by the smoked or i.v. route at least 6 times over the participant's lifetime prior to clinic intake (Day -3) and at least one use (smoked, i.v., or nasal route) within the past 3 months.
5. Provide a urine sample positive for cocaine at least once during screening (Days -28 to -4) and a urine test negative for cocaine at clinic intake.
6. Be able to verbalize understanding of consent form, able to provide written informed consent, and verbalize willingness to complete study procedures.
7. A female study participant must meet one of the following criteria:
  - If of childbearing potential – agrees to use one of the accepted contraceptive regimens from at least 30 days prior to the first administration of the study medication, during the study, and for at least 30 days after the last dose of the study medication. An acceptable method of contraception includes one of the following:
    - i. Abstinence from heterosexual intercourse
    - ii. Hormonal contraceptives (oral/injectable/implant/insertable hormonal birth control products, transdermal patch)
    - iii. Intrauterine device (with or without hormones)OR agrees to use a double barrier method (*e.g.*, condom and spermicide) during the study and for at least 30 days after the last dose of the study medication.
  - If a female of non-childbearing potential – should be surgically sterile (*i.e.*, has undergone complete hysterectomy, bilateral oophorectomy, or tubal ligation/occlusion) or in a menopausal state (at least 1 year without menses), as confirmed by FSH levels ( $\geq 40$  mIU/mL).A male study participant that engages in sexual activity that has the risk of pregnancy must agree to use a double barrier method (*e.g.*, condom and spermicide) and agree to not donate sperm during the study and for at least 90 days after the last dose of the study medication.
8. Be able to comply with protocol requirements, rules and regulations of the study site, and be likely to complete all the study treatments.

## 7.2 Exclusion Criteria

In order to participate in the study, participants must not:

1. Have a current or past history of seizure disorder, including alcohol- or stimulant-related seizure, febrile seizure, or significant family history of idiopathic seizure disorder.
2. Have any previous medically adverse reaction to cocaine, including loss of consciousness, chest pain, paranoid reaction, or seizure.
3. Have clinically significant findings in the opinion of an investigator based on the MINI (version 7.0) neuropsychiatric interview.
4. Be pregnant or lactating.
5. Have a sitting systolic blood pressure > 140 mmHg, diastolic blood pressure > 90 mmHg and heart rate > 100 beats per minute at screening and clinic intake.\*
6. Have current or lifetime past history of cardiac illness, including, but not limited to:
  - a) Uncontrolled arrhythmia
  - b) Congestive heart failure (CHF)
  - c) Myocardial infarction
  - d) Uncontrolled symptomatic angina
  - e) QTcF >450 msec for males and females or history of prolonged QT syndrome.
7. Have a history of liver disease or current elevation of aspartate aminotransferase (AST), alanine aminotransferase (ALT),  $2 \times$  the upper limit of normal.\*
8. Have a lifetime history of renal disease or current renal function test values\* as follows:
  - blood urea nitrogen (BUN) >  $2 \times$  the upper limit of normal, or
  - creatinine > 1.5 mg/dL
9. Blood donation (excluding plasma donation) of approximately 500 mL within 56 days prior to screening.
10. Plasma donation within 7 days prior to screening.
11. Treatment with an investigational drug within 30 days or 5 times the half-life (whichever is longer) prior to screening.
12. Have any clinically significant finding on medical history, physical examination, clinical laboratory test, vital signs or ECGs that contraindicate participation in the study.
13. Have a history of suicide attempts or current or recent evidence of suicidal ideation in the past 12 months based on the Columbia-Suicide Severity Rating Scale (C-SSRS).
14. Have a positive urine drug screen upon clinic intake (Day -3) for any of the following drugs: alcohol, amphetamine/methamphetamine, barbiturates, benzodiazepines, buprenorphine, cocaine, fentanyl, 3,4-methylenedioxymethamphetamine (MDMA), methadone, phencyclidine/phenylcyclohexyl piperidine (PCP), propoxyphene, and opioids (e.g., codeine, heroin, morphine, oxycodone, etc.). If a participant presents with a positive urine drug screen for cocaine or alcohol at clinic intake (Day -3), the participant may be rescheduled one time at the discretion of an investigator or designee as long as

clinic intake is within the total screening window. A positive tetrahydrocannabinol (THC) test is not exclusionary, but participant must show no impairment.

15. Have used any prescription drugs within 14 days of clinic intake or non-prescription drugs or herbal remedies within 7 days of clinic intake.
16. Be unable to distinguish between a 20 mg and 40 mg dose of cocaine i.v. based on the high effects VAS at either the 5 or 10 minute time point during the screening infusion.
17. Have a positive serology for Hepatitis B surface antigen (HBsAg), Hepatitis C antibody (HCVab), or human immunodeficiency virus (HIV).
18. Have positive results for a coronavirus disease 2019 (COVID-19) test performed on Day -3 after screening is complete and participant is confirmed, but prior to admission.

\* Participants with an out-of-range laboratory test or vital signs may have the assessment repeated once, at the discretion of the PI.

## 8 INVESTIGATIONAL PRODUCT

### 8.1 SXC-2023

SXC-2023 is manufactured and supplied by Promentis Pharmaceuticals. The product is supplied as enteric capsules containing 200 mg of SXC-2023 (supplied in Size 0 white capsules). In addition to SXC-2023, the capsules contained the following inactive ingredients: microcrystalline cellulose, lactose monohydrate, methocel E3, croscarmellose sodium, and magnesium stearate.

Initial stability evaluations of the drug substance and drug product indicate that SXC-2023 is stable at room temperature and requires no special protection or handling; special protection from light is not required. The bottled drug product should be stored at 20-25°C with excursions allowed between 10°C and 30°C.

Participants will take four capsules of 200 mg SXC-2023 (total 800 mg) orally QD as described in Section 6. SXC-2023 will be administered to participants before regular breakfast. Any unused drug will be disposed according to standard practices.

### 8.2 Placebo

Matching placebo capsules will be supplied by Promentis Pharmaceuticals. The capsules should be stored at 20-25°C with excursions permitted to 10°C to 30°C.

### 8.3 Cocaine

Cocaine hydrochloride solution, 20 mg/mL in 4 mL vial (*i.e.*, 80 mg/vial) is manufactured by Murty Pharmaceuticals Inc. (Lexington, KY) under a contract with NIDA. The cocaine hydrochloride solutions should be stored in a securely locked refrigerator within the pharmacy. Standard controlled substance procedures will govern access to the drug. Cocaine will be

administered by 2 ml i.v. push over 60 seconds by an investigator or qualified designee (such as a licensed registered nurse). Any unused drug will be disposed according to standard practices.

#### **8.4 Dietary and Other Restrictions**

**Diet.** Food and drink will be provided by the site. From Days 3 to 9, SXC-2023 capsules will be administered to patients before regular breakfast. The first infusions of cocaine on Days 8 and 9 will be started 3 hours after SXC-2023 dosing. During infusion Sessions 1 to 5, caffeinated beverages are not permitted from 1 hour prior to and until 4 hours after cocaine administration; other beverages are allowed. Eating is not allowed during infusion to avoid risk of nausea/vomiting. A meal can be given at the end of an infusion session if they are stable without restriction.

**Exercise.** Participants will be instructed to refrain from participation in contact sports and weightlifting from 48 hours before inpatient period until completion of the study.

**Tobacco Products.** Participants will be allowed to smoke during the study in designated areas and accompanied by site staff at scheduled times according to the rules of the site. Smoking is permitted *ad libitum* and there is no restriction on the number of cigarettes smoked daily. However, during infusion sessions, smoking is not permitted from at least 1 hour prior to the first cocaine/saline infusion to until 4 hours after the second infusion.

**Alcohol.** Participants will be questioned about their estimated daily intake of alcohol during the pre- study evaluation of eligibility. Any participant who shows physiological dependence on alcohol requiring medical detoxification will be excluded. Alcoholic beverages are not permitted from 48 hours before the inpatient period until the discharge from the study. Participants will have a urine alcohol test on admission (Day -3). If a participant has a urine alcohol result greater than zero, the participant may be retested one time prior to screening infusion.

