each session. The participants will receive either SXC-2023 800 mg or matched placebo once a day every morning from Days 3 to 9. On Day 8, participants will receive cocaine 20 mg infusion (Infusion Session 4) and on Day 9 will receive cocaine 40 mg (Infusion Session 5). Each cocaine infusion will be preceded or followed by saline i.v. infusion. The first infusion on Days 8 and 9 will begin approximately 3 hours after SXC-2023 or placebo. Each infusion will consist of a 2 mL i.v. push and will be administered 60 minutes apart. The order of the saline and cocaine infusions for each participant for Infusion Sessions 4 and 5 will be the same as the randomized order for Infusion Sessions 2 and 3, respectively. The participants will be discharged from the research clinic on Day 11, 2 days after the last infusion of cocaine (Infusion Session 5), and will have a telephone follow-up call between 7 and 10 days after clinic discharge.

The study schema is illustrated in [Figure 1](#) and the schedule of infusion sessions is shown in [Table 1](#).

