### **9.5 Infusion Session 2 (Day 1)**

The baseline infusion sessions (Sessions 2 and 3 – Study Days 1 and 2) provide cardiovascular effects, subjective responses, and PK data of cocaine in the absence of SXC-2023. During each baseline infusion session, each session will administer both cocaine and saline in a randomized order. Sessions 2 and 3 are randomized independently of one another. The participant's semi-supine blood pressure must be  $\leq 140$  mm Hg (systolic) and  $\leq 90$  mm Hg (diastolic), heart rate must be  $\leq 100$  beats per minute taken 15 and 30 minutes prior to the first cocaine infusion. If blood pressure or heart rate is elevated, it may be repeated one time to determine if the participant meets these criteria to receive an infusion. The participant's ECG taken in the half-hour (-30 minutes) prior to receiving any cocaine infusion must not have any clinically significant abnormal arrhythmia or interval changes. The pregnancy test must be negative before infusion.

The schedule of activities for infusion sessions are shown in [Table 4](#).

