## 10.5 Cardiovascular Assessments During Infusion Sessions

Before and after each i.v. infusion, the participant's physiologic responses will be closely monitored using repeated HR, BP, and ECG readings, assessed in semi-supine position.

During the Screening Infusion Session 1, BP and HR will be recorded at the following nominal time points relative to the first infusion of the day: -30, -15, 5, 10, 15, 20, 25, 30, 45, 55, 65, 70, 75, 80, 85, 90, 105, 115, 125, 130, 135, 140, 145, 150, 165, 180, 210, 240, 270, 300, 330 and 360 minutes. Out of range BP and HR collected during the first 180 minutes post-dose will be repeated if deemed necessary by an investigator. Continuous cardiac monitoring with telemetry beginning approximately 60 minutes before the first infusion until 4 hours after the last cocaine infusion. Twelve-lead ECG measurements will be recorded at -30 minutes and at 5, 10, 15, 30, 45, 65, 70, 75, 90, 105, 125, 130, 135, 150, 165, 180, and 360 minutes after the first infusion. Study personnel and staff will monitor participants for at least 1 hour after each infusion. Times for collection of ECG and vital signs are nominal times  $\pm 3$  minutes for the first 30 minutes after the infusion and  $\pm 5$  minutes at all other time points. ECG then vital signs will be collected first when multiple assessments are scheduled at the same nominal time.

During the baseline and treatment infusions (Sessions 2 to 5), BP and HR will be recorded at the following time points relative to the first infusion of the day: -30, -15, 5, 10, 15, 20, 25, 30, 45, 55, 65, 70, 75, 80, 85, 90, 105, 120, 150, 180, 210, 240, 270, and 300 minutes. Out of range BP and HR collected during the first 180 minutes post-dose will be repeated if deemed necessary by an investigator. Continuous cardiac monitoring with telemetry beginning approximately 60 minutes before the first infusion until 4 hours after the second infusion. Twelve-lead ECG measurements will be recorded at -30 minutes and at nominal 5, 10, 15, 30, 45, 65, 70, 75, 90, 120, 150, 180 and 300 minutes after the first infusion. Times for collection of ECG and vital signs are nominal times  $\pm 3$  minutes for the first 30 minutes after the infusion and  $\pm 5$  minutes at all other time points. ECG then vital signs will be collected first when multiple assessments are scheduled at the same nominal time.

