#### 7.4.2 Cardiovascular Responses

Summary statistics (n, mean, standard deviation, median, minimum and maximum) of HR and BP by treatment, cocaine dose, infusion session, and timepoint will be presented. Maximum, maximum change and time to maximum from pre-infusion during the first hour after each infusion will be summarized by treatment, cocaine dose, and infusion session.

The maximum value and maximum change from pre-infusion values will be analyzed using an analysis of covariance (ANCOVA) model to compare the treatment groups (SXC-2023 versus placebo). The ANCOVA model will include the baseline (i.e., prior to SXC-2023/placebo treatment) maximum value or the baseline maximum change from pre-infusion as a covariate. The analyses for the 20mg and 40mg cocaine infusions will be performed separately. Effects will be considered statistically significant at a two-sided  $p < 0.05$ .

The distribution of the maximum value and maximum change for HR and BP will be explored. If not deemed normal or if right skewed, an ANCOVA analysis will be performed on the log-transformed HR and BP maximum value and maximum change. If the log-transformed data distribution is not normal then a Wilcoxon rank sum test will be used to compare treatment groups.

Time to maximum value will be analyzed using a Kaplan-Meier estimator. A log-rank test will be used to compare the time to maximum value by treatment groups (SXC-2023 vs Placebo). The analyses for the 20mg and 40mg cocaine infusions will be performed separately. Effects will be considered statistically significant at a two-sided  $p < 0.05$ .

ECG parameters extracted from Holter and their changes from pre-infusion (mean of the 3 pre-infusion ECGs) will be presented with summary statistics by visit and timepoint. Changes in ECG intervals during saline infusion as compared to those taken during cocaine infusions will be also reported as summary statistics. A listing of clinically significant ECG changes will be presented.

Pulse will be summarized by infusion session, timepoint, and treatment group.

Clinically significant ECG values will be presented in listings.

A listing of repeated assessments will be presented.

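### The caffeine ban in Protocol 8.4 is timed from cocaine and the tobacco ban from the session's infusions, so read literally it covers the pre-infusion readings in only one of the two randomised orders

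*Protocol*

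**What the plan says.** Protocol 8.4 sets two intake rules for infusion sessions.

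- Caffeine, Sessions 1 to 5: "caffeinated beverages are not permitted from 1 hour prior to and until 4 hours after cocaine administration".
- Tobacco: "smoking is not permitted from at least 1 hour prior to the first cocaine/saline infusion to until 4 hours after the second infusion".

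The first rule is anchored on cocaine. The second is anchored on the infusions of the session, whichever of them is cocaine.

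In Sessions 2 to 5, "Infusions will be administered 60 minutes apart" (Protocol Table 1). At baseline, "each session will administer both cocaine and saline in a randomized order" (Protocol 9.5). The order in Sessions 4 and 5 "will be the same as the randomized order for Infusion Sessions 2 and 3, respectively" (Protocol 6). Session 1 has a fixed order: "20 mg cocaine, followed by a saline infusion, followed by 40 mg cocaine".

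Readings follow a different clock. Under Protocol 10.5, "BP and HR will be recorded at the following time points relative to the first infusion of the day". Protocol Table 4 places the ECG, VAS and BSCS on that clock too.

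For the primary cardiovascular comparison, SAP 7.4.2 states: "The maximum value and maximum change from pre-infusion values will be analyzed using an analysis of covariance (ANCOVA) model". The covariate is the corresponding value from the session before SXC-2023 or placebo. No other section of either document restricts caffeine.

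**The concern.** Cocaine falls at one of two times on the first-infusion clock, so a ban tied to cocaine produces two windows. They differ in the hour before the first infusion, when the session's reference readings are taken. A stimulant allowed before those readings in one order and barred in the other can shift HR, BP and the subjective baselines by order.

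Three features of the plan make such a shift hard to see or remove afterwards.

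- The cardiovascular ANCOVA in SAP 7.4.2 has no infusion-order term, although SAP 7.5.2.6 fits a second model with order for the PK parameters.
- Neither document provides for recording caffeine during sessions. Protocol 10.18 asks about xanthine products for eligibility only, whereas SAP 7.6.2 lists cigarette consumption.
- No stratification of infusion order by treatment arm is stated.

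At stake is added noise in a primary change score in a trial that requires only 8 completers per group. There is also a possible cue to the infusion order if the rule is applied to the letter.

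**Working it through.** The plan gives no figure to reproduce here. The check lays the ban windows over the reading times.

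**Inputs.** Cocaine at 0 min (cocaine-first) or 60 min (saline-first), from Table 1 and section 9.5. Readings in Sessions 2 to 5, from Table 4 and sections 10.5 and 10.21: 24 HR/BP (-30 to 300 min), 14 ECG (-30 to 300), 13 VAS (-30 to 120) and 2 BSCS (-5 and 125).

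**Windows.** Caffeine ban = cocaine time - 60 min to cocaine time + 240 min. Tobacco ban = 0 - 60 min to 60 + 240 min.

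| Sessions 2 to 5 | Ban (min) | Readings outside the ban |
|---|---|---|
| Caffeine, cocaine-first | -60 to 240 | HR/BP 270 and 300; ECG 300 |
| Caffeine, saline-first | 0 to 300 | HR/BP -30 and -15; ECG -30; VAS -30; BSCS -5 |
| Tobacco, either order | -60 to 300 | none |

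In both orders the literal rule leaves at least one caffeine-free hour before cocaine. The difference lies in the reference readings and the end of the session.

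**Which readings reach a test.** SAP 7.4.2 takes maxima within the first hour after each infusion, so the 270 and 300 min readings enter descriptive output only. The pre-infusion HR/BP readings do enter a test, through the change score. If caffeine raises the pre-infusion value and has worn off by the peak, the change score falls by that amount. If it persists in full, the change score is unaffected and the maximum value rises instead. The SAP does not say which reading is pre-infusion when cocaine comes second. If it were the 45 or 55 min reading, that lies inside the saline-first ban, and only carry-over from earlier caffeine could affect it.

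**Chance imbalance of order between arms.** Assume simple 1:1 allocation of order, independent of arm (not stated in the documents). The probability that the arms differ by 3 or more saline-first participants in a given session is 0.26 with 10 per arm and 0.21 with 8 per arm. For a difference of 4 or more with 10 per arm it is about 0.12.

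**Illustrative size.** Assume that caffeine raises pre-infusion systolic BP by d, from 0 to 10 mmHg, that every saline-first participant uses the allowance, and that the arms have 7/10 and 3/10 saline-first. The difference in mean pre-infusion value is (0.7 - 0.3) x d:

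- d = 0: 0 mmHg
- d = 5: 2 mmHg
- d = 10: 4 mmHg

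Order repeats in Sessions 4 and 5, so a stable shift enters both the covariate and the outcome. With covariate slope b, the part left in the adjusted comparison is (1 - b) x shift. At the 4 mmHg end this is 2 mmHg for b = 0.5 and 0.8 mmHg for b = 0.8 (both slopes assumed).

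**Session 1.** Cocaine is given at 0 and 120 min, so the caffeine ban runs from -60 to 120 + 240 = 360 min for everyone and covers every reading. The tobacco ban ends at 60 + 240 = 300 min, before the HR/BP readings at 330 and 360 min and the ECG at 360 min.

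**The case against.** The best defence is that the wording is shorthand. The protocol often writes cocaine where it means the first infusion of the session:

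- Section 8.4 itself places the first cocaine infusions on Days 8 and 9 three hours after dosing, while 9.7.1 and 9.7.2 give that interval to the first cocaine or saline infusion.
- Sections 9.5 (HR/BP), 10.4 (BSCS) and 10.21 (VAS) time readings from the cocaine infusion, where Table 4 times them from the first infusion. SAP 5.2.3.3 rewords the VAS timing accordingly.

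On that reading there is one window and no order effect. This is plausible. It does not settle the matter, because the tobacco rule in the same section does draw the distinction and nothing corrects the caffeine rule.

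A reader might also infer more than the documents support.

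- **That applying the rule must disclose the infusion order.** It need not. The rule is a prohibition, the site supplies all drinks, and a ban from -60 to 300 min for everyone satisfies both literal windows without knowledge of the order. Disclosure is possible only if the rule is applied to the letter. Masking of order in Sessions 2 to 5 is implied but never stated, and the order does not reveal the treatment arm.
- **That the treatment comparison is biased.** Order is randomised and repeated, so no arm is favoured by design, and the covariate takes up part of a stable shift.
- **That 4 mmHg is an expected effect.** It is the top of an assumed range, and it is a difference in pre-infusion values before adjustment.
- **That the late readings or the saline hour are exposed in the primary tests.** The late readings feed no test, and the saline hour lies inside the saline-first ban.

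**Conclusion.** The two rules in Protocol 8.4 use different anchors. Read literally, the caffeine rule leaves the pre-infusion HR/BP, ECG, VAS and BSCS readings unprotected for saline-first participants and protected for cocaine-first participants. This can add order-dependent noise to the reference for a primary change score.

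The size cannot be derived, because the documents give no caffeine effect. On the assumptions above it runs from nothing to 4 mmHg in arm-mean pre-infusion systolic BP, and less after covariate adjustment. The consequence also depends on the site following the literal wording, on saline-first participants taking caffeine in that hour, and on the session-start readings serving as the reference.

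This is an inexpensive improvement to the protocol. It does not undermine the primary analysis. The Session 1 tobacco wording is a minor, separate matter: it touches only late readings in a screening session before randomisation and has no bearing on the SXC-2023 versus placebo comparison.

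**What to change.** Reconcile the two rules in Protocol 8.4 by giving both the same session anchors: from at least 1 hour before the first infusion until 4 hours after the last infusion, whatever the order. In Sessions 2 to 5 both bans then run from -60 to 300 min, no scheduled HR/BP, ECG, VAS or BSCS reading falls outside them, and staff can apply them without knowing the order. Referring to the last infusion also reconciles the tobacco rule with the three infusions of Session 1, where its end moves from 300 to 360 min.

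The cost is two phrases in the protocol. In each of Sessions 2 to 5 a participant gives up one more hour of caffeine (-60 to 0 min if saline-first, 240 to 300 min if cocaine-first). Session 1 is unchanged for caffeine and one hour longer for tobacco. The SAP does not restate either rule, so it needs no edit, and the sample size is unaffected.
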